pacemaker and ICD (CRTd) has transformed heart failure treatment over the last decade, resulting in improved symptoms and quality of life, along with a reduction in hospitalisations and mortality (4, 5). Referral for implantation or battery/generator replacement remains guideline-driven (5, 6), with clinical indicators informing the decision (1, 7, 8). Clinical trials show a short-term improvement in patients' quality of life (9, 10) following ICD implantation, however for some people, the device has a detrimental impact on their psychological well-being and quality of life (11-13), particularly patients who receive frequent ICD shocks. Factors found to contribute to poor outcomes include Type D personality (14), poor illness perceptions (15), unrealistic expectations of treatment and underlying disease progression. Insufficient information can cause patients to misunderstand the functionality of their ICD, overestimating its benefits and prompting maladaptive coping strategies (16). American and Irish studies found 37% to 65% of patients with a recently implanted ICD, were unable to recall or inaccurately recalled the information professionals provided (17, 18). Similar results were noted in NI and Denmark regarding ICD deactivation (19, 20) as nearly half of patients surveyed (48%) reported they received no information. International guidelines state that providing patients with comprehensive information at the implantation stage is critical for ensuring the validity of informed consent (16, 18) as it facilitates an accurate understanding of the device capability and functionality now, and as the clinical condition progresses.

Identifying the evidence: Interventions to inform & support patients with ICD

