3. To explore the acceptability of the intervention through a questionnaire and focus groups with patients, family members and healthcare professionals.
4. To undertake a process evaluation identifying methodological issues, face and psychometric validity and the primary outcome for a future trial. Self-reported data from validated questionnaires delivered pre- and post-intervention will measure patients' knowledge, attitudes and experiences (EOL-ICD), device acceptance and concerns (ICDc and Florida Patient Acceptance Survey), quality of life (EuroQol-5D), anxiety (BAI) and illness perceptions. Caregivers will complete the carer strain index (CSI)

4: Trial design:

This CHOICE-ICD methodology is framed according to the Medical Research Council (MRC) framework (36), and in accordance with the Common Sense model of Self-regulation and previous research conducted by the experienced research team (19, 27, 37, 51-54).

Methods:

This study comprises of two phases, outlined in the Consort diagram (Figure 1) (55) and Gantt chart (Appendix 1) .

Phase 1: Co-design the intervention (Objective 1)

The co-design of the intervention involved a number of iterative steps (48). Previous work conducted by this research team developed the concept of an eHealth intervention. The first integrated workshop stakeholders (n=18; patients with an ICD, family members, cardiologists, heart failure nurses, cardiac physiologists, and software developers) was held on the 8th September 2023. Interaction focused on balancing technical, holistic and practical details, with the provision of clinical facts without evoking fear, in order to create a patient-centred learning environment. Unstructured meetings (online) were held with 10 stakeholders (patient, family members and professionals) who tested and provided feedback on the prototype of the APP, which was conveyed at the forthcoming stakeholder meeting. The prototype was tested at each

iterative stage for two weeks. Within the second stakeholder workshop (n=16), on the 22nd May, feedback from testers (n=8) informed the components of the APP, including content, patient videos, VR option, ease of use and navigation. The intervention was further optimised and the testers, over a 2-week period, invited to provide feedback.

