before obtaining written consent, baseline data is collected and 1:1 randomisation. Baseline questionnaires will be completed in all patients and caregivers recruited to the study. A convenience sample of $n=64$ patients will be randomised to the intervention and usual care, with $n=64$ receiving usual care alone, across Northern Ireland and Scotland. Patients and caregivers will be followed up at 3 months and 6 months' post intervention. Patients who received the Choice-ICD intervention, along with their caregivers and members of their clinical team (i.e heart failure nurse, cardiologist or cardiac physiologists) will be invited to participate in a focus group. Members of the clinical team (8-10) will be invited by the local collaborator ([name] or [name]) and if agreeable, contact details will be passed to the researcher to provide information on the study and obtain consent. Focus group will be conducted separately (Focus group 1: patients and caregivers Focus group 2: healthcare professionals) within each clinical site. Any patients, caregivers or healthcare professionals involved in Phase 1 (Co-design of the APP) will be excluded.

5: Power calculations:

Unpublished audit data show that in 2019/2020: 482 ICD/CRTD were implanted in NI and 250 implanted in Scotland. Given the total population size of 732 patients, we need to recruit 128 patients in total to account for an expected 10% attrition rate. This would leave a sample size of $n = 114$ (intervention, $n = 57$; control, $n = 57$) that enables us to estimate a recruitment rate of 50% to within a 90% confidence interval of $+\/- 10\%$, which should provide an accurate representation of the patient population. These statistics have been deemed suitable as higher precision would warrant a larger sample size, with the required resources being unsuitable for a feasibility study. Co-applicant (MD) will provide statistical support throughout. The results of the proposed study will enable the planning of a future definitive trial.

Table 1: Eligibility Criteria

Patient	Caregiver	Healthcare Professional
Patients with heart failure awaiting or with an ICD (no	Have contact with the patient at least 5 times per week.	Daily care of patients with heart failure and an implantable cardioverter

time restriction on implantation)		defibrillator
Aged 18 years and over	Aged 18 and over.	Willing to provide written informed consent

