No cognitive impairment	Be nominated by the patient.	Involved in the care of a patient using the Choice-ICD App
Willing to provide written informed consent	Be physically and mentally capable of participation (self-assessment)	
	Willing to provide written informed consent.	

Exclusion criteria:

- Patients, judged by their Cardiologist as physically or mentally unsuitable to complete the study.
- Patients or caregivers lacking capacity to give consent.
- Patients who have known pregnancy
- Caregivers who's patient is unwilling to take participate

6: Intervention:

Patients and family members will receive the online intervention (accessed via a password protected link) and British Heart Foundation (BHF) booklet: "Implantable Cardioverter Defibrillators" (2018- HIS19/1117) or the BHF booklet only (usual care group). The eHealth intervention is theoretically driven, interactive and provides personalised information to patients and family members when and where they wish to access it. Topics include: "How does an ICD work? How will it affect my daily activities? What do I do if I experience a shock? Do I have choices ahead when my health declines?" Each topic will have a link to a printable fact sheet with a prompt card that patients can take with them to their next professional consultation. Five short (2-3 minutes) videos, involving patients, caregivers and professionals, developed with MacMillen Media, will be uploaded onto the APP, alongside animation clips and useful links to online resources (56). A discussion forum will be accessible for participants using the APP,

which will be closely moderated by the researcher, who will ensure any concerning posts or dialogue are promptly removed, and the necessary action is taken. The diary function will allow patients to record and be reminded of future appointments. This detail will not be collected, but rather is for the patient's use only. The intervention is both an informational support resource as well as a "prompt" for patients and professionals to engage in complex discussions. Patients and family members will engage with the intervention for 3 months.

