if the patient lives in Clydebank. Data will be collected month 3, including system usability scale, and again at month 6 (post intervention). Questionnaires will be disseminated in paper copy. At 3 and 6 months, a stamped addressed envelope will be provided to promote return of the questionnaires to the researcher at QUB (LH). Reasons regarding loss to follow-up will be monitored. Primary outcome measures are the feasibility, acceptability and usability (according to SUS) of the intervention. Secondary outcome measures are effect of the eHealth intervention on patients' knowledge, anxiety and device related quality of life as measured by the questionnaires. (Appendix 2)

All data collected will be monitored by the Chief Investigator to ensure ethical, legal or management issues arising are addressed promptly. The researcher (LH) alongside her team, have experience and publications in this area (LD, DF, MD, OS). Results from the study will be reported back to participants and inform the intervention in preparation for a larger future trial.

8: Data Analysis

Descriptive and inferential data analysis will be conducted by LH using SPSS (IDM Statistics 22), which will focus on calculating effect sizes that describe the differences between pre- and post-intervention. Sub-group analysis will be undertaken between patients implanted with an ICD for the first time and those with a pre-existing device. Qualitative data will be collected from two focus groups with patients and family members (n=20) at 3 months by the RA. Results will enrich understanding of the perceptions of patients and family members towards the intervention and its acceptability, the validated tools used and how the intervention may facilitate future deactivation conversations. Barriers and facilitators of the intervention will be openly discussed. A brief acceptability questionnaire will be completed (64). Two separate focus group with healthcare professionals (n=20) will enable an insight into their perspectives towards the intervention. Each focus group will be audio-recorded, transcribed verbatim and thematically analysed. The transcript will be independently analysed to improve rigour and consistency.

9: Trial Monitoring:

The study will also be monitored periodically by members of the International steering group, who will assess the progress of the study, verify adherence to the protocol and national requirements, and review the completeness, accuracy and consistency of the data.

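### Section 8 centres the analysis on pre-to-post change and names no contrast between the randomised arms, so the stated quantity is not the effect of the intervention that the secondary outcome asks for

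*Protocol*

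**What the plan says.** - **Design.** Section 4 (Phase 2) describes consent, then "before obtaining written consent, baseline data is collected and 1:1 randomisation". It allocates 64 patients to the intervention plus usual care and 64 to usual care alone. Everyone completes baseline questionnaires, and both arms are followed at 3 and 6 months.
- **Target.** Section 7 states: "Secondary outcome measures are effect of the eHealth intervention on" patients' knowledge, anxiety and device-related quality of life.
- **Analysis.** Section 8 covers the descriptive and inferential analysis in one sentence, "which will focus on calculating effect sizes that describe the differences between pre- and post-intervention". The only comparison of groups that it names is a subgroup one, first-time implants against patients who already had a device. That is a baseline characteristic, not the randomised allocation.
- **Objective 4.** Section 3 uses similar wording: "Self-reported data from validated questionnaires delivered pre- and post-intervention will measure" the patient-reported outcomes.

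The protocol contains no statement that intervention and usual care will be compared on any questionnaire.

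**The concern.** In a randomised trial the effect of the intervention is the difference between the arms. Change from before to after also includes everything that would have happened without the website.

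The protocol gives reasons to expect such change. Both arms receive the BHF booklet (Section 6). Table 1 admits "Patients with heart failure awaiting or with an ICD", so some patients may be implanted during follow-up. Section 2 reports short-term gains in quality of life after implantation, "however for some people, the device has a detrimental impact on their psychological well-being and quality of life". The direction of any drift is therefore unknown.

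An analyst who followed Section 8 literally would leave the control arm unused for the secondary outcomes. Change over time could be reported as an effect of the website, or a real effect could be masked if usual-care patients worsen. Section 5 adds that "The results of the proposed study will enable the planning of a future definitive trial". If pre-to-post effect sizes were carried into that planning, the next trial could be too large or too small.

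**Working it through.** **Inputs from the protocol.** 64 patients are randomised per arm, and 57 per arm remain after 10% attrition (Section 5). This reproduces: 57 / 0.9 = 63.3, rounded up to 64 per arm, 128 in total. A less favourable case uses the 60% completion target in Appendix 2: 0.60 × 64 = 38.4, taken as 38 per arm. The protocol gives no figure for a questionnaire comparison, so there is none to reproduce.

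**Assumptions (not in the protocol).** Scores are in SD units with equal SDs at both times. The baseline to follow-up correlation r is 0.6 (range 0.5 to 0.7). The same drift occurs in both arms. Tests are two-sided at 5%.

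**Step 1: what each quantity estimates.**
- Change in the intervention arm = drift + effect
- Change in the usual-care arm = drift
- Difference between arms = effect

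**Step 2: true effect zero.** The SD of change is √(2(1 − r)) = √0.8 = 0.894. With n = 57 its standard error is 0.894/√57 = 0.118. Rejection rates for the paired t-test, from the noncentral t distribution:

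| Drift, either direction (SD) | n = 57, r = 0.6 | n = 57, r = 0.5 to 0.7 | n = 38, r = 0.6 |
|---|---|---|---|
| 0 | 5% | 5% | 5% |
| 0.1 | 13% | 12–16% | 10% |
| 0.2 | 38% | 32–48% | 27% |
| 0.3 | 70% | 60–82% | 52% |

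Simulation (20,000 trials per setting, drift from −0.3 to +0.3 SD) agreed with the pre-to-post rates within 0.01. The baseline-adjusted comparison of arms rejected in 4.7% to 5.3% of trials, with a mean estimate of 0.00.

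**Step 3: a real effect that is hidden.** Take a true effect of +0.3 SD and a drift of −0.3 SD, with n = 57 per arm. The pre-to-post change averages 0.3 − 0.3 = 0 and rejects in 5% of trials. The baseline-adjusted arm difference averages 0.30 and rejects in 51%.

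**Step 4: if the estimate were used for sizing.** Suppose the true effect is 0.3 SD and the next trial is a two-sample t-test with 80% power.

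| Drift (SD) | Apparent effect (SD) | Per arm | Actual power at 0.3 SD |
|---|---|---|---|
| −0.1 | 0.2 | 394 | 99% |
| 0 | 0.3 | 176 | 80% |
| +0.1 | 0.4 | 100 | 56% |

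**Step 5: precision of the arm comparison.** The 95% half-width is 1.96 × √((2/n)(1 − r²)).
- n = 57: 0.29 SD at r = 0.6 (0.32 at r = 0.5, 0.26 at r = 0.7)
- n = 38: 0.36 SD at r = 0.6 (0.39 at r = 0.5, 0.32 at r = 0.7)
- Unadjusted, 1.96 × √(2/n): 0.37 SD at n = 57 and 0.45 SD at n = 38

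**The case against.** The best defence is that the protocol uses pre- and post-intervention as labels for timepoints in both arms. Section 4 applies the post-intervention label to follow-up without restricting it to one arm, and Appendix 2 applies it to all consented participants. On that reading Section 8 names change scores, and the randomised design together with the Section 7 outcome implies that they will be compared by arm. A focus on one quantity does not exclude another.

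This softens the point but does not remove it. Change computed in both arms is still change over time. Reported separately, the two changes are drift + effect and drift. Pooled 1:1, they give drift + half the effect. Only their difference is the effect, and no sentence asks for it.

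Several narrower objections stand in part:

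- Model form and covariates can be left to an SAP, and none was available here. The choice of contrast is different, because Section 8 itself states one that does not match the outcome.
- Objective 4 says when questionnaires are given and what they measure. It is weak support for the concern.
- Section 8 names no paired test and no 5% level, so the rejection rates illustrate the bias and do not predict a planned test.
- Nothing says that questionnaire effect sizes will set the size of the next trial, so Step 4 is conditional. With baseline adjustment at r = 0.6 the 176 would become 176 × (1 − 0.36) ≈ 113. The other sizes shrink by the same factor, so the relative error is unchanged.
- The 38-per-arm case treats a success threshold as the number analysed, whereas Section 5 expects 10% attrition.

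**Conclusion.** The concern holds and should be fixed. The contrast stated in Section 8 does not estimate the secondary outcome stated in Section 7 unless usual-care patients show no change, in which case the bias is zero. The mismatch follows from the wording and needs no numerical assumption. Its size does: under the assumptions above, and with no true effect, a drift of 0.2 SD would produce a nominally significant within-arm change in roughly a third to a half of trials with 57 in the arm. The direction of the bias cannot be known in advance.

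The reach is limited. Feasibility, acceptability and usability are the primary outcomes, and neither they nor the progression rules depend on this sentence. What is exposed is the interpretation of the secondary outcomes and any effect size taken from them into a later trial.

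**What to change.** Replace the sentence in Section 8 with wording such as:

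> For each questionnaire the estimate of interest is the between-arm difference (intervention minus usual care) at 3 and 6 months, analysed as randomised and adjusted for the baseline score, with 95% confidence intervals. Within-arm changes from baseline are descriptive only.

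If the sponsor already intends to compare change by arm, this makes it explicit. The essential part is naming the arm contrast; the model details may sit in the SAP. The emphasis on estimates with intervals suits a feasibility study that was not sized to test these outcomes.

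The cost is one protocol sentence, changed before analysis. All the data are already being collected. The price is wider intervals: about ±0.29 SD for the adjusted arm difference, against 1.96 × 0.118 ≈ ±0.23 SD for change within one arm, both at 57 per arm and r = 0.6. Reported effects may also look smaller than raw change if patients improve under usual care.

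### Month-3 focus groups, offered only to intervention-arm patients and caregivers, partly confound the month-6 effect sizes, and nothing requires the month-3 questionnaires to be returned first

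*Protocol*

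**What the plan says.** Section 4 (Phase 2) defines who is invited: "Patients who received the Choice-ICD intervention, along with their caregivers and members of their clinical team". It describes no matching contact for the usual-care arm. The same section sets the format: "Focus group will be conducted separately (Focus group 1: patients and caregivers Focus group 2: healthcare professionals) within each clinical site".

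Section 8 fixes timing and size: "Qualitative data will be collected from two focus groups with patients and family members (n=20) at 3 months by the RA". The stated purpose covers views of the intervention, views of the questionnaires, and "how the intervention may facilitate future deactivation conversations".

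On follow-up, section 4 says "Patients and caregivers will be followed up at 3 months and 6 months' post intervention", and section 7 says "Data will be collected month 3, including system usability scale, and again at month 6 (post intervention". Section 6 sets the period of use: "Patients and family members will engage with the intervention for 3 months".

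Section 7 makes feasibility, acceptability and usability (by the SUS) the primary outcomes. The effect of the website on patients' knowledge, anxiety and device-related quality of life is secondary. The instruments include the EOL-ICDQ (end-of-life experiences, attitudes and knowledge) and the Beck Anxiety Inventory. The month-3 and month-6 forms are on paper and come back in a stamped addressed envelope.

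**The concern.** At month 3 some intervention-arm patients and caregivers sit in a facilitated group that discusses the outcome instruments and deactivation. Three months later they complete the same instruments, one of which measures end-of-life knowledge and attitudes. The usual-care arm has no comparable contact. Any effect of the session on later answers appears in one arm only and is counted as an effect of the website.

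A second gap concerns month 3 itself. The forms are posted back and no order is fixed, so an attendee could complete the month-3 questionnaires after hearing the group discuss barriers, facilitators and the tools. This includes the SUS, which measures a primary outcome.

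At stake are the secondary effect sizes, mainly at month 6, and the independence of some month-3 usability ratings. The protocol itself fixes the invitees and the timing, so this is not a detail that an analysis plan alone could settle.

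**Working it through.** **Sequence.** I read months as counted from the start of use, because the Abstract and section 7 list baseline, 3 and 6 months.

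| Time | Intervention arm | Usual-care arm |
|---|---|---|
| Baseline | Questionnaires | Questionnaires |
| Months 0–3 | Website and booklet | Booklet |
| Month 3 | Questionnaires, SUS; focus group for some (order not fixed) | Questionnaires |
| Month 6 | Questionnaires | Questionnaires |

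The month-6 forms follow the group, and the group exists in one arm only.

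**Inputs.**
- 64 randomised and 57 retained per arm (sections 4 and 5).
- 20 patients and family members over two groups (section 8). I take 20 as the total. The parallel text for professionals (two groups, n=20; 8–10 clinical team members invited) fits that reading. The split between patients and family members is not given.
- The effect of attendance on a patient's month-6 score is not in the protocol. I assume 0.2 to 0.5 SD.

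**The plan's own figure.** For a 50% rate, 90% confidence and a half-width of 10 points, n = 1.645² × 0.25 / 0.10² = 67.6. A finite-population correction on 732/2 = 366 per arm (the split is my assumption) gives 67.6 / (1 + 66.6/366) = 57.2. That matches 57 per arm and 114 in total; 114/0.9 = 126.7, so 127, or 128 when made even. I use 57 only as the denominator.

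**Share exposed.**
- Half of the attendees are patients: 10/57 = 17.5% (10/64 = 15.6% of those randomised).
- All attendees are patients (upper bound): 20/57 = 35.1% (20/64 = 31.3%).

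So between 37/57 = 65% and 47/57 = 82% of retained intervention patients reach month 6 without having attended.

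**Shift in the arm mean** = share exposed × effect per attendee.

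| Effect per attendee (assumed) | 10 patients | 20 patients (bound) |
|---|---|---|
| 0.2 SD | 0.175 × 0.2 = 0.04 SD | 0.351 × 0.2 = 0.07 SD |
| 0.5 SD | 0.175 × 0.5 = 0.09 SD | 0.351 × 0.5 = 0.18 SD |

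**Yardstick.** The standard error of a between-arm difference is √(2/57) = 0.187 SD (95% half-width 1.96 × 0.187 = 0.37 SD). With 10 patients the shift is 0.035/0.187 = 0.19 to 0.088/0.187 = 0.47 standard errors. The direction is not known: talking about deactivation could raise or lower anxiety.

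**The case against.** The strongest case against is that this is a feasibility study. Its primary outcomes are feasibility, acceptability and usability, and no progression rule in Appendix 2 uses an effect size. Section 8 describes pre- to post-intervention effect sizes and names no month-6 between-arm estimate. The groups evaluate the website; they do not teach deactivation. The website already contains a discussion forum, patient videos and a topic on choices when health declines, so peer exchange is not foreign to it. All of this stands, and it limits the weight of the point. It does not remove it, because a change from baseline to month 6 in the intervention arm carries the same shift.

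Two stronger readings are tempting. A reader might infer that the month-6 comparison tests website plus group discussion instead of the website. The protocol does not support that, since at least about 65% of retained intervention patients would never attend a group. A reader might also infer that the month-6 effect size will set the size of the definitive trial. Section 5 says only that the results will allow such a trial to be planned.

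Moving the groups past month 6 is also less simple than it looks. It would delay acceptability data, which are primary, by up to three months. Section 6 ties the optional Belfast virtual-reality session to the focus-group occasion, so that part of the intervention would fall after every outcome measurement unless a separate visit were added. This objection stands and shapes the fix.

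**Conclusion.** The point holds in a limited form. Month-6 effect sizes are partly confounded by focus-group attendance in a minority of the intervention arm and cannot be fully credited to the website. The likely shift is small: about 0.04 to 0.09 SD with 10 patients attending, up to half a standard error of the between-arm difference. The larger figures (35% exposed, up to 0.18 SD) need every attendee to be a patient, although the protocol describes mixed groups.

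These sizes rest on three assumptions: 20 attendees in total, a half-and-half split, and a per-attendee effect of 0.2 to 0.5 SD, which the protocol does not give. The one-arm invitation and the timing do not depend on them.

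The month-3 results are free of this problem only if each attendee's forms come back before the group, and the protocol does not require that.

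**What to change.** Keep the month-3 groups and change four things in sections 7 and 8:

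1. Require each attendee, patient or caregiver, to return the month-3 questionnaires, and patients the SUS, before attending. Handing them in on arrival would do.
2. Name month 3, the end of the 3-month period of use, as the main time point for the effect sizes.
3. Record who attended.
4. Report month 6 as secondary, with a sensitivity analysis that excludes attendees' post-group data. State that attendees are self-selected and are removed from one arm only, so the exclusion may itself introduce selection bias.

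The cost is small: month 6 becomes a supporting time point and one sensitivity analysis is added, with no extra visits. Holding the groups after the month-6 forms is an option but not the preferred one, because it delays acceptability data and would also move the Belfast virtual-reality session.
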